Trained chart abstractors will review each chart to complete the chart abstraction templates with the information requested. They will not be making a direct determination of care quality or efficiency, but rather obtaining the information for a computerized algorithm that will do this. A WH specialist will be available to them to answer questions that may arise. We will develop a database (using REDcap software) so that data may be entered directly into REDcap via a study computer. Senior research staff who are clinicians will randomly spot-check chart abstraction data, throughout the data collection period, to verify adherence to study protocols.

Independent Variables: *DWHP characteristics* may influence the quality and efficiency of the care that they provide, as well as their response to the intervention. We will extract DWHP characteristics from the Personnel and Accounting Integrated Data System (PAID) Master File, which contains the human resources data for all VA employees, including provider gender, age, education and licensure (MD, NP, PA), and medical specialty. We will obtain *characteristics of patients* seen by the DWHP in the study period from VA administrative data. This data will include: female caseload (# of uniques) and workload (# of encounters), female percent of total caseload and workload. We will derive percent of female workload by age category (<45, 45-64, 65+, corresponding to reproductive age group, age for emergence of chronic conditions, and older).

Aim #1 Statistical Analysis: We will calculate descriptive statistics of the proportion of CBOC women's primary care that is guideline-adherent. We will examine each of these descriptive statistics by clinical condition, and conduct z-tests for differences in proportions between conditions. We will also evaluate a series of logistic regressions to test for association of the composite measure of quality with each of the various independent variables in order to build a predictive model. Because of the hierarchical nature of the data (episode of care within patient within DWHP), a generalized linear model (GLM) approach using a logit link will be used to estimate and test the significance of the regression coefficients.

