For the analysis of the intervention effect over time, we will conduct a modified stepped-wedge analysis. This analysis takes into account the hierarchical nature of the data, with episodes of care occurring over time, and being nested within DWHPs. In the stepped wedge analysis, calendar time is divided into steps, corresponding to the time periods when providers are initially exposed to the intervention.

Sample Size and Power Calculations: The power calculations are predicated on the goal of evaluating the performance of DWHPs through the episodes of care they see. There are two levels of clustering: DWHPs within healthcare systems and episodes of care within DWHPs. We are making the assumption that there is little or no correlation between the DWHPs. As a result, we performed the calculations via the single level of clustering within DWHPs, with the episode of care as the unit of analysis. We will assume two values for the intra-cluster correlation coefficient (ICC): 0.03 and 0.05. The latter is relatively large compared to results that have been reported in the literature. The calculations assume a two-tailed 5% significance level and power of 80% to detect a difference between the study arms (with the study arm referring to intervention versus control, and including all data collection in each of those study periods, respectively). The statistical test involved is a simple z-test for the comparison of two proportions, but the actual analysis will be more sophisticated using covariates and adjusting for the actual number of episodes seen by a given DWHP. Thus, it can be assumed that the sample size calculations presented here are conservative.

With a baseline estimate from our preliminary data that 67% of episodes of care are fully proficient, then with 25 episodes of care per DWHP, we could detect small to medium effects of the intervention (see Table 2). If the baseline proficiency was 80%, then we could detect a medium size intervention effect, whereas if the baseline proficiency was 50%, we could detect a very small effect. If we increased the number of eligible episodes of care from which to measure proficiency to 50 per DWHP, then with a baseline proficiency of 67%, we could detect a small intervention effect. The number of available DWHPs (approximately 20 per study arm) and episodes of care provides us with >80% power.

Table 2: Number of DWHPs needed to detect the effects in each scenario with 80% power

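### The Aim 1 association models answer clustering with a plain GLM and name no method that accounts for it; fitted literally, tests of provider-level covariates would have a type I error of about 13% to 29%

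*Combined protocol and SAP*

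**What the plan says.** Under Aim #1 Statistical Analysis, the combined protocol and SAP plans "a series of logistic regressions to test for association of the composite measure of quality with each of the various independent variables", as steps towards a predictive model. The data are described there as having three levels, with episodes inside patients inside DWHPs, and for that reason "a generalized linear model (GLM) approach using a logit link will be used to estimate and test the significance of the regression coefficients". Nothing there or elsewhere adds a random effect, a working correlation or a cluster-robust variance.

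The covariates are listed under Independent Variables. They include "provider gender, age, education and licensure (MD, NP, PA), and medical specialty", together with each DWHP's female caseload, workload and age mix. These describe the provider, so they take one value, or nearly one, for all of that provider's episodes.

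The intervention effect has its own paragraph, which plans a stepped-wedge analysis in modified form and states: "This analysis takes into account the hierarchical nature of the data, with episodes of care occurring over time, and being nested within DWHPs". No mechanism is given.

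The Sample Size and Power Calculations section says "There are two levels of clustering: DWHPs within healthcare systems and episodes of care within DWHPs". It then assumes negligible correlation between DWHPs and works with the single level of episodes within DWHP, at ICCs of 0.03 and 0.05.

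**The concern.** The plan gives a reason for its model that the named model does not meet. A GLM in the ordinary sense treats all episodes as independent given the covariates. If episodes of the same DWHP are correlated, as the power section assumes, the standard error of any coefficient for a provider trait is too small. Most listed covariates are of that kind.

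The stake is which provider characteristics are reported as associated with guideline-adherent care and kept in the predictive model. With about 20 DWHPs there are only about 20 independent observations on any such trait, however many hundreds of episodes are abstracted.

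**Working it through.** **Inputs, all from Sample Size and Power Calculations and Table 2.** Two-sided 5% level and 80% power; ICC 0.03 or 0.05; m = 25 or 50 episodes per DWHP; baseline 67% (alternatives 80% and 50%); about 20 DWHPs per study arm.

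**Step 1: reproduce Table 2.** Take the two-proportion sample size (pooled variance under the null, no continuity correction), multiply by the design effect DE = 1 + (m − 1) × ICC, divide by m and round up. For 67% v 77%, n = 316 episodes per arm before clustering:
- m = 25, ICC 0.03: 316 × 1.72 / 25 = 21.74, so 22 (table: 22)
- m = 25, ICC 0.05: 316 × 2.20 / 25 = 27.81, so 28 (table: 28)
- m = 50, ICC 0.03: 316 × 2.47 / 50 = 15.61, so 16 (table: 16)
- m = 50, ICC 0.05: 316 × 3.45 / 50 = 21.80, so 22 (table: 22)

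Over the whole table, 14 of 16 cells match exactly. The other two (10.03 printed as 10, 20.06 printed as 20) differ only in rounding. The sample size therefore does allow for clustering within DWHP, through this design effect.

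**Step 2: apply the same design effect to a test that ignores clustering.** For a covariate constant within DWHP, the independence-based standard error is too small by a factor √DE. The true two-sided error of a nominal 5% test is 2 × [1 − Φ(1.96 / √DE)].

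| m | ICC | DE | √DE | Type I error |
|---|---|---|---|---|
| 25 | 0.03 | 1.72 | 1.31 | 13.5% |
| 25 | 0.05 | 2.20 | 1.48 | 18.6% |
| 50 | 0.03 | 2.47 | 1.57 | 21.2% |
| 50 | 0.05 | 3.45 | 1.86 | 29.1% |

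**Step 3: check by simulation.** Outcomes were beta-binomial with mean 67%, with 20 or 40 DWHPs, a null covariate splitting them in half, and 10,000 runs per setting. Ranges are over the eight combinations of DWHP number, m and ICC.
- Ordinary logistic regression, provider-level covariate: 13.3% to 29.8%.
- Ordinary logistic regression, covariate balanced within DWHP: 4.0% to 4.8%, so no inflation.
- Sandwich variance clustered on DWHP, z reference: 5.9% to 7.9%. With 20 DWHPs alone it is 7.5% to 7.9%.
- The same with a small-sample factor (K/2)/(K/2 − 1) on the variance and a t reference on K − 2 degrees of freedom, where K is the number of DWHPs: 4.6% to 5.5%.

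**Sensitivity (assumed values, not in the plan).** With ICC 0.01, the step 2 formula gives 7.8% at m = 25 (DE 1.24) and 10.8% at m = 50 (DE 1.49). Table 2 counts episodes per study arm. If 50 per arm were pooled over both periods into m = 100, the errors would be 32.5% at ICC 0.03 (DE 3.97) and 42.2% at ICC 0.05 (DE 5.95).

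**The case against.** The strongest reply is that the authors plainly mean to handle clustering. They choose the approach because the data are hierarchical, the power section applies a DWHP-level ICC, and that section promises an actual analysis more refined than a z-test. The GLM label may be loose shorthand for a generalized linear mixed model or GEE. This stands as far as it goes. A reader might infer that provider effects will certainly be declared significant too often, but the documents support only the conditional statement: they would be if the named model were fitted. The reply does not remove the problem, because an analyst working from the text alone would fit ordinary logistic regression.

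A second reply is that these regressions are secondary. That also stands. A reader might infer that the intervention test is equally compromised. The documents do not say that the GLM is reused there, and they say that analysis accounts for nesting. Any error rate for the intervention term would depend on the number of healthcare systems and the spread of episodes over steps, which the plan does not give.

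A reader might also infer that the patient level has been dropped, since the stepped-wedge paragraph speaks only of episodes "with episodes of care occurring over time, and being nested within DWHPs". But that wording does not exclude patients, and the two-level statement belongs to an openly simplified power calculation. Variance clustered on DWHP would also absorb correlation among one woman's episodes with the same provider. The plan gives no figure for episodes per woman or for correlation within a woman, so no size can be put on this.

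**Conclusion.** The point holds as a defect of specification that should be fixed before analysis. The model named for the association and predictive regressions does not do what it was chosen to do, and no other text supplies the missing part.

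If the text is followed literally, type I error for provider-level covariates is about 13% to 29% instead of 5%, roughly three to six times nominal. This rests on the plan's own ICCs and episode counts, equal numbers of episodes per DWHP, and covariates constant within DWHP. It does not extend to covariates balanced within a DWHP, and it does not establish any error in the intervention test. For that test, the gap is only that the means of accounting for nesting is unnamed.

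**What to change.** Under Aim #1 Statistical Analysis, replace the GLM wording with a method that handles clustering. Two choices would serve:
- mixed-effects logistic regression with a random intercept for DWHP, and one for patient where women contribute several episodes; or
- logistic regression by GEE, or with cluster-robust variance, clustered on DWHP.

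With either, specify a small-sample correction and a t reference with degrees of freedom based on the number of DWHPs. With so few DWHPs, a plain sandwich z-test still gives about 6% to 8%.

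Name the same clustering method in the stepped-wedge paragraph. State the levels consistently there and in the association models, including how the healthcare-system level is treated.

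The cost is a few sentences of SAP text and a different estimation command. No design or data-collection change is needed. The downside is wider intervals for provider traits, which reflect the information that about 20 DWHPs can give.

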This proposed research project was developed in partnership with VA Patient Care Services' Women's Health Services (WHS) and Specialty Care Services (SCS), VISN 22, and VA Greater Los Angeles Healthcare System. It will impact VA practice and policies in women Veterans' health care, access, and quality (HSR&D priority areas) as well as other specialty areas. Further, it will advance science in both WH care quality measurement and the delivery of health care through non-face-to-face interactions.

Research Design and Methods

Study Design and Overview: We propose to conduct a prospective, modified stepped wedge trial of *DWHP Support* for DWHPs in healthcare systems that participate in Gynecology SCAN-ECHO and have gynecology e-consults. To accommodate facility and VISN needs, we will work with our facility and women's health partners to stage the assignments for the stepped wedge rollout (i.e., it will not be randomized). We will introduce the intervention throughout one healthcare system at each step, with the intervention being directed to all DWHPs in that healthcare system.

We will use a mixed methods analytic approach to measure the intervention's effect, while also evaluating the

implementation processes and use of the intervention. Therefore, while testing *DWHP Support* effectiveness, this study will also advance our understanding of the context for its implementation, which can support its broad implementation in VA, as well as inform future trials. An advantage of our modified stepped wedge approach is that our intervention will occur in the "real world", i.e., not in a highly controlled experimental setting; this enhances the potential external validity of the intervention and thereby increases the possibility that the intervention could feasibly be spread to other VISNs, should it prove effective.

Setting and Participants: *DWHP Support* will be implemented in healthcare systems in VISN 22 and at other VA sites nationally. VISN 22 encompasses Southern California and the Las Vegas area. It has a racially and ethnically diverse women Veteran population, with 68% non-Hispanic White, 5% non-Hispanic Black, 21% Hispanic, and 6% other racial/ethnic groups.⁴⁵ The participants will be DWHPs in those settings.

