We hypothesize that *DWHP Support* will improve the quality and efficiency of WH care in CBOCs. We expect that these effects may be influenced by baseline characteristics of the DWHPs (e.g., time in practice), patient conditions and characteristics, and practice characteristics, as well as DWHPs' use of the intervention. For this aim, our analytic sample will be limited to sites participating in DWHP Support outside of GLA, given that DWHP support was piloted in GLA and therefore does not have a recent "control" period (i.e., GLA was contaminated by the pilot). We will, however, use GLA data to pilot our electronic medical record (EMR) data abstraction procedures. We will also collect GLA e-consult data because this data were not contaminated by the piloting of SCAN-ECHO at GLA.

Dependent Variables: The main outcome measures will be quality of care defined by adherence to practice guidelines. We will assess quality of care and efficiency of care using the VA electronic medical records (EMR) of all female patients seen by DWHPs during the data collection period. With the modified stepped wedge design, each participating site healthcare system is contributing data to both intervention and control periods, thereby addressing comparability concerns. We expect to identify multiple episodes of care per DWHP over the combined data collection periods, where we define an episode of care as the care initiated by the DWHP for a WH condition, irrespective of whether it occurs over one or multiple encounters, and is face-to-face or not.⁵⁴

Electronic medical record (EMR) data abstraction: To assemble the relevant data from the EMR using the VHA Health Information Access (HIA) program's Data Use Agreement protocols, we will use the *Corporate Data Warehouse (CDW)*, accessed through VINCI and discussed above and, as needed, the Compensation and

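### The stepped-wedge test states clustering only within DWHPs although whole healthcare systems cross over; if a system's DWHPs shift together over time, its standard error is too small

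*Combined protocol and SAP*

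**What the plan says.** - **Rollout (Study Design and Overview).** "We will introduce the intervention throughout one healthcare system at each step", with all DWHPs in that system exposed at once. The unit that crosses over is therefore the healthcare system.
- **Sites.** Under Setting and Participants, the intervention "will be implemented in healthcare systems in VISN 22 and at other VA sites nationally". Under Specific Aim #1, "our analytic sample will be limited to sites participating in DWHP Support outside of GLA". The number of systems left in the analysis is not given.
- **Stepped-wedge test (Aim #1 Statistical Analysis).** "This analysis takes into account the hierarchical nature of the data, with episodes of care occurring over time, and being nested within DWHPs". Time enters because "calendar time is divided into steps". No estimator is named, and neither a system effect nor a system-by-period effect is mentioned.
- **Regression models (same section).** The structure is similar, the "hierarchical nature of the data (episode of care within patient within DWHP" being the stated reason for the modelling approach.
- **Sample Size and Power Calculations.** "There are two levels of clustering: DWHPs within healthcare systems and episodes of care within DWHPs". The section then takes the correlation between DWHPs as little or none and calculates with clustering inside DWHPs only. It expects the real analysis to be more elaborate, which it describes as using covariates and allowing for each DWHP's episode count.

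**The concern.** DWHPs in one system can be affected together in a given period, for example by a staffing change or local training. Because all of them cross over at the same step, such a shift is partly confounded with the intervention effect and adds to its variance. Step terms remove only what is common to all systems. Fixed system effects remove only what is constant over time. A deviation specific to one system in one period survives both, and a model with clustering only at the DWHP treats those providers as independent evidence. The test affected is that of the main aim.

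**Working it through.** **Inputs from the plan (sample-size section and Table 2):** two-sided 5% level; DWHP ICC 0.03 (0.05 also considered); 25 or 50 episodes per DWHP per study arm; about 20 DWHPs per arm; 67% versus 77%. Each system contributes to both phases, so 25 per arm means 50 episodes per DWHP in total.

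**Assumed, because the documents are silent:** S systems (3 to 10) and S+1 periods, one system crossing per step; DWHPs and episodes spread evenly; system-by-period ICC ρ from 0 to 0.02.

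**1. Reproduce Table 2.** For 67% v 77%, n = [1.96√(2×0.72×0.28) + 0.8416√(0.67×0.33 + 0.77×0.23)]²/0.10² = 315.3, so 316 episodes per arm. Multiply by [1+(m−1)ICC]/m:
- m=25: 316×1.72/25 = 21.74; 316×2.20/25 = 27.81
- m=50: 316×2.47/50 = 15.61; 316×3.45/50 = 21.80

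Rounded up, these are the printed 22, 28, 16 and 22. Table 2 therefore carries DWHP clustering and nothing at system level.

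**2. Standard error from a DWHP-only model, crediting the plan with step and fixed system effects.** Let v = 0.67×0.33 = 0.2211. The 20×50 = 1,000 episodes fall in S(S+1) system-by-period cells, so the variance of a cell proportion is w = 0.97·v·S(S+1)/1000. The DWHP intercepts are absorbed by the system effects. After removing step and system, the intervention indicator has sum of squares Q = (S−1)(S+2)/12. Then SE = √(w/Q). For S=4: w = 0.00429, Q = 1.5, SE = 0.0535.

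**3. Add the system-by-period variance ρv.** True SE = √((w+ρv)/Q). For S=4 and ρ=0.01: √((0.00429+0.00221)/1.5) = 0.0658, which is 1.23 times the model SE. In general, ratio² = 1 + 1000ρ/[0.97·S(S+1)], and the true level is 2[1−Φ(1.96/ratio)]:

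| Systems | ρ=0 | 0.002 | 0.005 | 0.01 | 0.02 |
|---|---|---|---|---|---|
| 3 | 5.0% | 7.0% | 10.1% | 15.1% | 23.5% |
| 4 | 5.0% | 6.2% | 8.1% | 11.1% | 16.9% |
| 6 | 5.0% | 5.6% | 6.4% | 7.9% | 10.8% |
| 10 | 5.0% | 5.2% | 5.5% | 6.1% | 7.2% |

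With 50 episodes per phase, replace 1000 by 2000. At ρ = 0.005/0.01/0.02 the level becomes 15/23/35% with 3 systems, 11/17/26% with 4 and 6/7/10% with 10. A DWHP ICC of 0.05 changes the 25-episode figures by at most 0.3 point.

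**4. Checks by simulation of binary data, no true effect, ρ = 0/0.005/0.01/0.02.**
- Fitted mixed model with DWHP effects only, 1,200 replicates: 4.7/9.3/14.1/22.9% (3 systems), 5.5/6.8/9.0/14.8% (4), 3.9/5.9/8.4/9.6% (6). Most values are a little below the formula; the pattern is the same.
- Logistic GEE clustered on DWHP with step effects but no system effects, 4 systems, 1,500 replicates: 6.0/7.9/10.5/15.5% with model-based errors and 8.2/10.9/13.2/17.2% with robust errors. Robust errors at DWHP level do not repair the problem.

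**The case against.** **The faulty model is inferred.** No estimator is named, the text does not say that the hierarchy ends at the DWHP, and the plan shows that it knows of the system level. This stands in part: the documents do not prove that a DWHP-only standard error will be reported. But the only hierarchy stated for the test is the DWHP one. The promised refinements, covariates and episode counts, are not a system-level component. That each system serves in both phases deals with stable differences between systems, not with shifts in one period.

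**Size rests on unknowns.** This stands. Sites beyond VISN 22 are planned, so 3-5 systems is not shown to be the likely case, and no ICC at this level is available. With zero correlation the 5% level holds.

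**Stronger readings.** A reader might infer that the test is certainly anti-conservative; the documents do not support that, since it needs both a DWHP-only analysis and a positive correlation. A reader might also draw in the non-random rollout order ("stage the assignments for the stepped wedge rollout (i.e., it will not be randomized"). That is a separate question of bias; it does not make the standard error wrong, and the change proposed here would not address it.

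**A system-level regression has costs of its own.** It loses more power when systems differ in size, it must say how covariates are kept, and its degrees of freedom depend on the number of periods. These points stand and are built into the fix.

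**Conclusion.** The concern holds conditionally. Following the stated hierarchy gives too small a standard error whenever DWHPs in a system shift together over time, and the plan gives no figure to show that they do not. With 20 DWHPs, 25 episodes per DWHP per phase and equal systems, the true level of a 5% test is about 8-15% for 3-4 systems at system-by-period ICC 0.005-0.01. It is about 5-7% for 10 systems (ICC up to 0.02), or for ICC of 0.002 or less. More episodes per DWHP make it worse. The number of systems largely decides whether this matters, and the plan does not state it. It should be fixed before analysis; confidence is moderate because both governing quantities are assumed.

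**What to change.** In the stepped-wedge paragraph of Aim #1 Statistical Analysis:

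1. State the number of healthcare systems in the analysis (outside GLA) and the number of periods.
2. Add the healthcare system as a clustering level, with fixed effects for intervention, calendar step and system.
3. Base the test on inference that allows for system-by-period variation, with a named small-sample method.
   - **Few systems:** one valid choice is a regression of covariate-adjusted system-by-step proportions, with t on cells minus fitted parameters. With S+1 periods this is S(S+1) − (2S+1) = S²−S−1. State how unequal systems are weighted. In simulation with equal systems (20,000 replicates, 3-10 systems, ICC 0-0.02) the unadjusted version held 4.6-5.5%.
   - **About six or more systems:** an alternative is a mixed logistic model with DWHP and system-by-period random effects and a small-sample correction. Only a linear version was simulated. With 3-4 systems at ICC 0.01 it estimated the system-by-period variance as about zero in 27% of samples, so it is less suitable there.

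**Cost.** SAP wording and little programming; no new data. Intervals widen: with 4 equal systems and ICC 0.01, the 95% half-width goes from 1.96×0.0535 = 10.5 points to 2.201×0.0658 = 14.5 points (11 df). If the correlation is zero, power for 67% v 77% falls from 46% to 40% with 4 equal systems (0.10/0.0535 = 1.87; normal, then noncentral t on 11 df). With 3 it falls from 44% to 31% (0.10/0.0556 = 1.80; 5 df). With 10 the loss is from 50% to 49%. Unweighted regression with unequal systems has less: about 31-34% for 4 systems of 8/6/4/2 DWHPs and 25-29% for 11/5/2/2.

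### Table 2 sizes a parallel two-group z-test, but the planned analysis is a stepped wedge: with calendar-step terms, the power claimed at 25 episodes per arm is optimistic for some effects, though not all.

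*Combined protocol and SAP*

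**What the plan says.** In the combined protocol and SAP, the Sample Size and Power Calculations section sets the error rates: "The calculations assume a two-tailed 5% significance level and power of 80% to detect a difference between the study arms". The method is given as follows: "The statistical test involved is a simple z-test for the comparison of two proportions, but the actual analysis will be more sophisticated using covariates". Clustering is handled at DWHP level only ("We are making the assumption that there is little or no correlation between the DWHPs"), and "We will assume two values for the intra-cluster correlation coefficient (ICC): 0.03 and 0.05". The section calls the result conservative because the real analysis will be more elaborate, and says that about 20 DWHPs per arm give power above 80%. It does not say for which effect. It contains no term for step or period.

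The design is described elsewhere. Study Design and Overview has one healthcare system starting at each step, without randomisation. Specific Aim #1, Dependent Variables, says that "each participating site healthcare system is contributing data to both intervention and control periods". Aim #1 Statistical Analysis says that "calendar time is divided into steps, corresponding to the time periods when providers are initially exposed to the intervention". The number of systems is not given, and no stepped-wedge model is written out.

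**The concern.** The calculation and the analysis answer different questions. Table 2 compares two groups of DWHPs measured side by side. In the trial, one set of DWHPs moves from control to intervention, and the later a period is, the more systems are exposed. Exposure and calendar step are therefore strongly correlated.

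Two forces then pull in opposite directions. Using each DWHP as his or her own control removes between-DWHP variation and raises power. Estimating step effects takes away much of the information on the intervention and lowers it. The plan's inference that a more elaborate analysis can only help overlooks the second force.

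If the second force is the larger, some effects that Table 2 shows as detectable with 20 DWHPs are not detectable at 80% power, and a null result could be misread as evidence of no effect.

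**Working it through.** **Inputs.** From the Sample Size section and Table 2: two-sided 5%, 80% power, ICC 0.03 and 0.05, 25 or 50 episodes per DWHP per arm, four pairs of proportions, about 20 DWHPs, no correlation between DWHPs. The 67% baseline is the plan's own preliminary estimate ("With a baseline estimate from our preliminary data that 67% of episodes of care are fully proficient"). Assumed here: 3 to 8 systems.

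**Step 1: reproduce Table 2.** DWHPs per arm = (1.96 + 0.8416)² × [p1(1-p1) + p2(1-p2)] / (p2-p1)² × [1 + (m-1) × ICC] / m, rounded up.

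Example, 50% to 63%, m = 25, ICC 0.05: 7.849 × (0.2500 + 0.2331) / 0.0169 = 224.4 episodes; design effect 1 + 24 × 0.05 = 2.2; 224.4 × 2.2 / 25 = 19.74, so 20. Table 2 prints 20. All 16 cells match, so Table 2 is a calculation for two independent groups.

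**Step 2: power of that test with 20 DWHPs per arm.** Same example: SE = √(0.4831 × 2.2 / 500) = 0.0461; 0.13 / 0.0461 - 1.96 = 0.86; power 0.805.

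**Step 3: power under a stepped wedge.** Generalised least squares on the proportion scale, with:
- S systems and S + 1 equal periods, one system switching per step;
- step fixed effects and a DWHP random intercept;
- total variance equal to the mean of p1(1-p1) and p2(1-p2);
- no system-level correlation, as the plan assumes;
- 20 DWHPs in total, each with 50 episodes spread evenly over the periods. This gives 25 per arm on average, not exactly 25 for every DWHP.

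Same example with S = 4: the SE is 0.0508, so 0.13 / 0.0508 - 1.96 = 0.60 and power is 0.73. Without the step terms the SE is 0.0328 and power is 0.98.

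Power at 25 episodes per arm on average (ICC 0.03 / 0.05; ranges run over 3 to 8 systems):

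| Effect | Two-group z-test | Stepped wedge with step effects |
|---|---|---|
| 80% to 90% | 0.93 / 0.85 | 0.76-0.84 / 0.74-0.82 |
| 67% to 83% | 0.99 / 0.98 | 0.94-0.98 / 0.93-0.97 |
| 67% to 77% | 0.77 / 0.67 | 0.56-0.65 / 0.54-0.63 |
| 50% to 63% | 0.89 / 0.81 | 0.70-0.79 / 0.69-0.77 |

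**Step 4: locate the cause.** Dropping the step terms from the same model gives about 0.91 or more in every row. The loss therefore comes from separating the effect from calendar step, not from reusing the DWHPs.

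**Step 5: sensitivity.**
- Exactly 25 control and 25 intervention episodes for every DWHP: 67% to 77% falls to 0.46-0.55 and 80% to 90% to 0.65-0.75.
- Number of systems, 67% to 77%: about 0.45 with two systems and still only 0.65-0.68 with 20.
- A linear time trend in place of step effects gave essentially the same power for 2 to 6 steps.
- A logistic simulation with DWHP fixed effects (4 steps, ICC 0.05) gave 0.66, 0.92, 0.49 and 0.62 for the four rows in table order. These are lower than the figures above and point the same way.
- 50 episodes per arm on average, 67% to 77%: 0.81-0.89, with 16-20 / 17-20 DWHPs needed against Table 2's 16 / 22. With exactly 50 and 50, power is 0.73-0.82.

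**The case against.** **No step term is written.** The plan speaks of a modified stepped-wedge analysis and specifies no model. If no time term is fitted, Table 2 is indeed conservative. This stands as a limit, because the reversal rests wholly on the step term. But dividing calendar time into steps is hard to read otherwise, and in a staged, non-randomised rollout an analysis without time would confound the intervention with secular change.

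**About 20 per arm might mean 40 DWHPs.** With 40 DWHPs sharing the same 1,000 episodes (25 each), power for 67% to 77% is 0.59-0.69 / 0.58-0.67, so little changes. With 40 DWHPs each averaging 25 episodes per arm (2,000 episodes), it is 0.85-0.91 / 0.83-0.90. Since every system contributes to both periods, the reading of the same 20 DWHPs is the more natural, but the plan should say so.

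**The 67% to 77% row is not promised at 25 episodes.** Table 2 itself asks for 22 / 28 DWHPs there, more than the 20 available. This is right: the shortfall is visible in the table before any step term, and the step term widens it. The accompanying text does, however, claim small to medium effects at 25 episodes.

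**Stronger readings.** A reader might infer that Table 2 is miscalculated. It is not; every cell reproduces. A reader might also infer that the claim of more than 80% power fails throughout. It does not: 67% to 83% holds comfortably, and 80% to 90% exceeds 80% in 7 of the 12 combinations of system count and ICC.

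**Conclusion.** The concern holds as a mismatch between the sizing and the planned analysis. At 25 episodes per arm with step effects estimated, 50% to 63% is below 80% power for every system count from 3 to 8, although Table 2 shows it as reachable with 16 / 20 DWHPs. The 80% to 90% row depends on the number of systems, the 67% to 77% gap widens, and 67% to 83% is safe. Neither the statement that the calculation is conservative nor the unqualified power claim is supported.

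The figures are illustrative. They rest on 20 DWHPs in total, 3 to 8 systems, equal periods, a DWHP random intercept and no system-level correlation. The size of the loss also depends on how episodes fall across periods. The conclusion is specific to 25 episodes: at 50 per arm on average, the need for 67% to 77% is close to or below Table 2's, depending on the ICC.

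**What to change.** Recompute Table 2 for the stepped-wedge model, using the actual number of systems, DWHPs per system and episodes per DWHP per period, with step fixed effects and a DWHP random intercept. Delete the sentence calling the calculation conservative. Replace the single power statement with the power for each effect. State that about 20 DWHPs is the total if the same DWHPs are in both arms. If no step term is intended, say so and justify it.

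The cost is one recalculation and less favourable stated figures. Abstracting 50 episodes per arm would recover much of the power but is optional: with 20 DWHPs it doubles chart abstraction from about 1,000 episodes (20 × 50) to about 2,000 (20 × 100), and it does not guarantee 80% for 67% to 77% if episodes are split exactly evenly.
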